8.2 Baseline Assessments

After signing the ICF, demographic and anthropometric information will be assessed to describe the participants. Age at enrollment, race, ethnicity, income, education, marital status, year of type 2 diagnosis, gender identity, biological sex, weight, height, etc. will be collected at baseline.

Baseline assessments also include a 14-day, blinded CGM assessment using the FreeStyle Libre Pro system. The FreeStyle Libre Pro system (sensor and reader) is commercially available and will be used according to user manual instructions; however, the system will be started at home by the participant instead of in a clinic with an HCP. The sensor will be returned to the clinical site for data download. A minimum of five days of blinded Libre Pro CGM sensor data must be obtained for randomization. Participants will use the provided reader to confirm adequate days of data recording during the Baseline assessment period.

All 14-day, blinded, FreeStyle Libre Pro sensors will be returned via mail. Data will be uploaded with a FreeStyle Libre Pro reader using the Libre 2 algorithm and then downloaded to secure study computer. Blinded FreeStyle Libre Pro sensors will be tracked by linking sensor serial numbers with study participant ID numbers.

Once baseline assessments are complete, the study intervention (use of CGM vs. BGM) begins concurrently with the initiation of the WFKD (Day 0).

8.3 Outcome Assessments

Outcome-related measures will be assessed at Baseline, Month 1, Month 2, Month 3, and Month 6. Primary and secondary outcome assessments will occur after the intervention, the “Post-Dietary Change” period, which is approximately Day 90 to 104. Additional secondary and exploratory outcome assessments will occur after “Follow-Up” period, which is approximately Day 180 to 194.

The study will include five defined Contact Periods between study staff (Virta and IDC) and study participants (“Baseline”, “Month 1”, “Month 2”, “Month 3”, and “Month 6”). Each Contact Period will last approximately two to three weeks, to accommodate the 14-day sensor wear. Required assessments can take place anytime during the Contact Period. Each Contact Period includes a plus or minus 10 or 14 day window, depending on the period; however, this should minimally impact the length of study participation since assessment windows are set according to initiation of the WFKD at Day 0. For example, assessment activities during Contact Period Two could start as early as day 20 or end as late as Day 54 and be in-window; and the target start date for Contact Period Three would remain at Day 90 regardless of when Contact Period Two was completed.

CGM vs. BGM to Optimize Glycemic Outcomes in T2D Following the Virta Treatment Ver. 2.0 06Dec2022

Outcome measures will be assessed using study-specific glucose and ketone testing supplies, which will be provided by Abbott Diabetes Care, the manufacturer of these products. Supplies will be mailed to each participant from the IDC after consent is signed and throughout the study as needed. All application and start-up of the FreeStyle Libre Pro and FreeStyle Libre 2 systems will be done independently by the participant with manufacturer- and study-provided resources for support.

Participant supplies include:

- Blinded 14-day FreeStyle Libre Pro system with sensors and reader
- Personal 14-day FreeStyle Libre 2 system with the associated phone-based Libre 2 app
- Precision Xtra Blood Glucose & Ketone Monitoring System with glucose and ketone test strips
- Lancing devices with lancets
- Supply return kits

Personal 14-day Libre 2 data will be collected at multiple assessment points throughout the study for CGM arm participants. The 14-day Libre 2 data are retrieved electronically from the FreeStyle Libre2 app, which is sent to the LibreView website. Data is automatically uploaded to LibreView when the subject's smartphone is connected to the internet. Data will be downloaded from LibreView by staff at the specified intervals for outcome assessment purposes.

Participants will be instructed to contact the Virta care team for study-related questions, healthcare-related questions, and any adverse events. Care related to the treatment of adverse events associated with study-supplied devices may be recommended. Medical care that does not pertain to diabetes management will not be provided to study participants as a part of this protocol. Participants will be instructed to contact IDC for problems related to study-provided monitoring supplies. IDC may contact participants directly for device-related issues and for questions/issues related to outcome assessments (e.g. survey data, blinded sensor data, etc.). IDC will maintain accountability records for study-specific glucose and ketone monitoring supplies including dates and quantity of product issued to participants.

8.4 Contact Schedule

Contact period	Key tasks
#1: Baseline Assessments: Day -21 to -1	
● Eligibility confirmed and consent conducted and documented● Participant receives baseline study supplies and instructions for completing baseline assessments, including HbA1c, in the mail● Participant is randomized once they confirm that the minimum of five days of Libre Pro CGM data has been recorded. If a participant is not able to obtain a minimum of five days of blinded CGM data, they will be provided an option to repeat the blinded sensor wear period or choose to withdraw.● Participants who capture five or six days of blinded CGM data on the first sensor may be provided an option to wear a repeat blinded CGM sensor to collect additional blinded CGM data. Wearing a repeat sensor, if 5 or 6 days of blinded sensor data was obtained on first sensor, is not required for randomization.● Participant continues wearing 14-day blinded CGM sensor and promptly mails sensor(s) back for data capture

	
 ○ Note: Participants randomized to the CGM arm will be instructed to return the blinded CGM sensor(s) and the associated reader. ● Plan initiation of the WFKD ● Participant receives study supplies according to randomization assignment in preparation for initiation of study intervention ● Baseline assessments are documented 
Note: There may be several days between Day -1 and Day 0 to account for participant readiness to begin the program; final clearance by the Virta care team (i.e. standard process); supply shipping issues; or personal factors for the participant (e.g. scheduling, medication adjustment, CGM wear issues). In other words, Day -21 to Day -1 will include initiation of baseline assessments, and Day 0 will mark the actual start of the program. All baseline assessments must be completed before Day 0. The difference between Day -1 and Day 0 will be as short as possible; Investigator discretion will be used to determine an inappropriate delay between study Day -1 and Day 0.


#2: Month 1 Assessment: Day 30 to 44 with up to +/- 10 days
 
Intervention Period
	
 ● Participants complete month 1 assessments ● BGM group: 
 ○ Prompted to apply and start Libre Pro CGM for 14-day wear ○ Participant confirms five days of blinded CGM data has been recorded. If a participant is not able to obtain a minimum of five days of blinded CGM data, they will be provided an option to repeat the blinded sensor wear period. ○ Participant promptly mails blinded CGM sensor back for data capture ● CGM group: 
 ○ Maintains consistent personal Libre 2 use for 14 days ○ HCP documents CGM data review and shares learnings with participant asynchronously ● Additional glucose and ketone monitoring supplies sent as needed ● Month 1 assessments are documented

#3: Month 2 Assessment: Day 60 to 74 with up to +/- 10 days
 
Intervention Period
	
 ● Participants complete month 2 assessments ● BGM group: 
 ○ Prompted to apply and start Libre Pro CGM for 14-day wear ○ Participant confirms five days of blinded CGM data has been recorded. If a participant is not able to obtain a minimum of five days of blinded CGM data, they will be provided an option to repeat the blinded sensor wear period. ○ Participant promptly mails blinded CGM sensor back for data capture

CGM vs. BGM to Optimize Glycemic Outcomes in T2D Following the Virta Treatment Ver. 2.0 06Dec2022

	
 ● CGM group: 
 ○ Maintains consistent personal Libre 2 use for 14 days ○ HCP documents CGM data review and shares learnings with participant asynchronously ● Additional glucose and ketone monitoring supplies sent as needed ● Month 2 assessments are documented
#4: Month 3 Assessment: Day 90 to 104 with up to +/- 10 days Intervention Period	
 ● Participants complete month 3 assessments, including HbA1c ● BGM group: 
 ○ Prompted to apply and start Libre Pro CGM for 14-day wear ○ Participant confirms five days of blinded CGM data has been recorded. ○ If a participant captures less than 7 days of blinded CGM data, they will be provided an option to wear a repeat blinded CGM to collect additional blinded CGM data. ○ Participant promptly mails blinded CGM sensor(s) back for data capture ● CGM group: 
 ○ Maintains consistent personal Libre 2 use for 14 days ○ HCP documents CGM data review and shares learnings with participant asynchronously ● Additional glucose and ketone monitoring supplies sent as needed ● Month 3 assessments are documented
#5: Month 6 Assessment: Day 180 to 194 with up to +/- 14 days Follow-Up Period	
 ● Participants complete month 6 assessments, including HbA1c ● BGM group: 
 ○ Prompted to apply and start Libre Pro CGM for 14-day wear ○ Participant confirms five days of blinded CGM data has been recorded. ○ If a participant captures less than 7 days of blinded CGM data, they will be provided an option to wear a repeat blinded CGM to collect additional blinded CGM data. ○ Participant promptly mails blinded CGM sensor(s) back for data capture ● CGM group: 
 ○ Maintains consistent personal Libre 2 use for 14 days ○ HCP documents CGM data review and shares learnings with participant asynchronously ● Month 6 assessments are documented 
Note: The month 6 assessment is the final study contact. Participants in the BGM arm will be required to return all blinded Libre Pro CGM sensors and the associated reader promptly after study completion. Participants will not be required to return any other study-provided glucose or ketone monitoring supplies at the end of the study.

9 Early Termination and Participant Withdrawal

A participant can choose to terminate study participation and exit the study at any time and for any reason. A participant can be withdrawn from the study without their consent if deemed necessary based on adverse event(s) or for any other reason deemed appropriate by Investigators, such as non-compliance with study instructions. If a participant chooses early termination or is withdrawn, the Investigators will decide whether the participant could be eligible to complete a final assessment.

Participants will be asked their reason for early withdrawal and reason for CGM discontinuation if applicable. Participants who terminate or are withdrawn early will be required to return used blinded Libre Pro CGM sensors and the associated Libre Pro reader promptly after study exit; they will not be required to return any other study-provided glucose or ketone monitoring supplies. Early termination or participant withdrawal will not impact participation in the Virta Treatment.

10 Lost to Follow-Up

Multiple attempts will be made to contact participants who become lost to follow-up. Investigator discretion will determine whether a participant should be withdrawn if reasonable attempts for contact are unsuccessful.

11 Protocol Deviation

A protocol deviation occurs when the study is not conducted according to this protocol. All deviations will be documented in study deviation log. Investigators will not knowingly deviate from this protocol except in the cases of protecting participant safety. The delegated Investigator will notify the IRB of protocol deviations in accordance with IRB policies and procedures.

12 Potential Risks and Benefits

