PWD	People with diabetes
SAE	Serious adverse event
SOC	Standards of Medical Care
SOP	Standard operating procedure
T2D	Type 2 diabetes
TIR	Time in range
TITR	Time in tight range
UAE	Unanticipated event
UPIRTSO	Unanticipated Problems Involving Risks to Subjects or Others
WFKD	Well-formulated ketogenic diet

2 Protocol Summary

Title:	Continuous Glucose Monitoring versus Blood Glucose Monitoring to Optimize Glycemic Outcomes in People with Type 2 Diabetes Following the Virta Carbohydrate-Restricted Treatment Program (IGNITE Study)
Population:	N=150; Adults \geq 18 years with T2D who are enrolled in the Virta Treatment
Intervention:	Use of CGM during participation in the Virta Treatment
Objectives:	
Primary: Difference in change in 14-day CGM-derived TIR (% time with glucose 70-180 mg/dL) from Baseline to 3-month Post-Dietary Change period between participants with T2D who are randomized to use either BGM or CGM as part of Virta Treatment.
 
Secondary:
 
 • Difference in 90-day mean blood ketone levels between BGM and CGM arms • Difference in changes in other CGM-derived metrics from Baseline to 3-month Post-Dietary Change period between BGM and CGM arms

	
• Difference in percent of participants reaching CGM-derived consensus targets at the end of the 3-month Post-Dietary Change period between BGM and CGM arms• Difference in Change in HbA1c from Baseline to the end of the 3-month Post-Dietary Change period between BGM and CGM arms
Design/Methodology:	Non-pivotal, randomized, parallel group, two-arm, prospective study. 1:1 randomization to either BGM or CGM during Baseline assessment period. See Appendix A for a study schematic and Appendix B for a table of study periods and assessments.
Total Study Duration:	Approximately 24 months
Subject Participation Duration:	Approximately 7-8 months

3 Background/Rationale and Purpose

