All participants must obtain Virta's standard medical approval from a Virta HCP and meet all eligibility criteria, as defined in Section 6, to participate in the study. Once the informed consent form (ICF) has been signed, the participant is formally enrolled in the study and a participant ID number will be assigned and recorded in the shared Virta and IDC study database (REDCap). Participants will be randomized 1:1 to either the BGM or CGM arm (Table 1) once a minimum of five days of blinded Libre Pro CGM data is confirmed by the participant. Of note, the blinded Libre Pro CGM system provides a way for the participant to see the number of days of data recording while the sensor is in use. If a participant wears a blinded Libre Pro CGM at baseline that does not capture at least 5 days of data, the participant will be provided the option to wear a repeat blinded CGM or choose to exit the study. Participants who capture five or six days of blinded CGM data may also be provided an option to wear a repeat blinded CGM to collect additional blinded CGM data.

Blinding procedures are not described since blinding is not possible in a study comparing two different methods of glucose monitoring (BGM versus CGM); the participants will know which arm they are assigned to in order to conduct the appropriate monitoring.

Given that enrolling participants takes several months to complete, a block randomization scheme will be used to ensure that participants are assigned to BGM and CGM arms in approximately equal proportions each month. The participant randomization schedule will be generated by the study statistician using the random number generator in SAS. Participants will remain in their assigned study arm throughout the intervention and follow-up period (day 0 to day 194).

Table 1. Randomization arms and associated study-arm devices

Study Arm	Devices Used
Blood Glucose Monitoring (BGM) Arm	Commercially approved FreeStyle Libre Pro Sensor and Reader (blinded CGM) Commercially approved Precision Xtra Blood Glucose & Ketone Monitoring System for glucose and ketone monitoring; used in accordance with package inserts.
Continuous Glucose Monitoring (CGM) Arm	Commercially approved FreeStyle Libre Pro Sensor and Reader (blinded CGM for baseline assessment only) Commercially approved 14-day, personal FreeStyle Libre 2 system and associated phone-based app; used in accordance with package inserts.

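### The baseline-data exclusion in section 15.1 also drops randomized participants whose mailed baseline sensor fails, even when they have a Month 3 TIR

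*Combined protocol and SAP*

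**What the plan says.** **Randomization.** The Protocol Summary (section 2) gives "1:1 randomization to either BGM or CGM during Baseline assessment period". Section 7.2 triggers it "once a minimum of five days of blinded Libre Pro CGM data is confirmed by the participant", and the contact schedule in 8.4 repeats this: "Participant is randomized once they confirm that the minimum of five days of Libre Pro CGM data has been recorded". The trial is open label: "the participants will know which arm they are assigned to in order to conduct the appropriate monitoring".

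**Retrieval of baseline data.** Under 8.2 the participant checks the number of recorded days on the supplied reader, and the data are downloaded once the sensor has come back by post. In 8.4, wear goes on after the randomization step: "Participant continues wearing 14-day blinded CGM sensor and promptly mails sensor(s) back for data capture". For a short first sensor, 8.4 adds: "Wearing a repeat sensor, if 5 or 6 days of blinded sensor data was obtained on first sensor, is not required for randomization".

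**Analysis.** Section 15.1 fits a linear mixed model to baseline and Month 3 TIR, with treatment, period and their interaction as fixed effects and patient as a random effect. It excludes enrolled participants with fewer than five days of baseline sensor data and allows two sensors from one contact period to be combined. It sets no cut-off at the randomization date. Section 7.2 fixes the meaning of enrolled: "Once the informed consent form (ICF) has been signed, the participant is formally enrolled in the study".

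**Sample size.** Section 15.5 plans on 150 randomized participants with adequate baseline data and 85% retention to Month 3. Section 7.2 expects 126 of the 150 to be evaluable, and defines evaluable as having at least five baseline sensor days.

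**The concern.** The condition for randomization (days shown on the reader) and the condition for analysis (days recovered from the returned sensor) are checked at different times and by different people. A sensor lost in the post or unreadable on arrival meets the first and fails the second. Because enrolment is defined by consent, the exclusion in 15.1 covers these randomized people too. It then acts as a post-randomization exclusion in an open-label trial, applied for a reason that does not prevent the participant from having a Month 3 TIR. A likelihood-based mixed model does not need a baseline value in order to use a Month 3 value, so the loss is avoidable.

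The same timing has a lesser consequence. Since randomization can come on day 5 of a 14-day wear, part of the baseline TIR may be recorded after the arm is assigned. Baseline TIR is an outcome in the 15.1 model, so an arm-specific shift on those days would enter the treatment-by-period contrast.

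**Working it through.** **1. The plan's own figure.** Inputs from 15.5: difference 10 TIR points, SD 20, two-sided alpha 0.05, power 80%.

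- n = 2 × (1.960 + 0.842)² × 20² / 10² = 62.8, so 63 per arm. This reproduces.
- 63 / 0.85 = 74.1, so about 75 per arm and 150 in total. This reproduces.
- The exact t-test needs 63.8, and its power at 63 per arm is 79.5%. The difference is immaterial.

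**2. Who is excluded.** Take 75 per arm and 85% retention (15.5) and a baseline failure rate f. The documents give no f, so 2%, 5% and 10% are assumptions. Dropped per arm: 75 × f = 1.5, 3.75 or 7.5. At f = 5% the groups per arm are:

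- both values: 75 × 0.95 × 0.85 = 60.6
- baseline only: 75 × 0.95 × 0.15 = 10.7
- Month 3 only: 75 × 0.05 × 0.85 = 3.2 (these are lost without need)
- neither: 75 × 0.05 × 0.15 = 0.6

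**3. Power with and without the exclusion.** Let r be the baseline-to-Month 3 correlation (assumed) and Σ the 2 × 2 covariance matrix with SD 20. The information per arm for the two period means is

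I = 75(1−f)(0.85)Σ⁻¹ + 75(1−f)(0.15)·diag(1/400, 0), plus 75f(0.85)·diag(0, 1/400) if Month 3-only participants are kept.

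SE = √(2c′I⁻¹c) with c = (−1, 1), and power ≈ Φ(10/SE − 1.96). At r = 0.5 and f = 5%, SE is 3.566 with exclusion (10/3.566 − 1.96 = 0.84, giving 80.1%) and 3.539 without (0.87, giving 80.7%).

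| r | f | No failures | With exclusion | Month 3-only kept |
|---|---|---|---|---|
| 0.5 | 2% | 82.1% | 81.3% | 81.5% |
| 0.5 | 5% | 82.1% | 80.1% | 80.7% |
| 0.5 | 10% | 82.1% | 77.9% | 79.2% |
| 0.3 | 5% | 68.8% | 66.6% | 67.5% |
| 0.7 | 5% | 95.8% | 94.9% | 95.1% |

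At r = 0.5 and f = 5%, keeping these participants restores about 0.6 of a 2.0-point loss. These figures use a normal approximation and include baseline-only participants, so they should be compared with each other and not with the 79.5% in step 1.

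**4. Baseline days after allocation.** The worst case assumes randomization and disclosure as soon as day 5 is recorded.

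- One sensor: (14 − 5)/14 = 9/14 = 64%. The share is 50% if randomized on day 7, 29% on day 10 and 0% on day 14.
- Pooled repeat sensor after a 5-day first sensor: 14/19 = 74%.
- Pooled repeat sensor after a 6-day first sensor, randomized at day 5: (1 + 14)/20 = 15/20 = 75%, the maximum.

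Bias = assumed arm-specific shift × share. The documents give no shift. For 0.5, 1 or 2 points the bias is 0.32, 0.64 or 1.29 on one sensor, and 0.38, 0.75 or 1.50 if every participant had the maximum pooled case. The SE of the difference in change at 63 per arm is 20√(2(1−r))·√(2/63) = 4.22, 3.56 or 2.76 for r = 0.3, 0.5 or 0.7. So 0.64 points is 0.15, 0.18 or 0.23 of a standard error.

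**5. Evaluable.** Five baseline days are the condition for randomization, so by the 7.2 definition all 150 would be evaluable at randomization. The 126 is 2 × 63, and is reached only through Month 3 retention: 150 × 0.85 = 127.5.

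**The case against.** **On the exclusion.** Section 8.2 already requires five days of data before randomization, and 15.5 counts only randomized participants with adequate baseline data. The rule can therefore be read as aimed at people never randomized. Failures after randomization may be few, and at 5% power remains 80.1%. All of this stands, and it limits the importance of the point. It does not change what the wording of 15.1 covers.

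A reader might go further and infer that the exclusion biases the result towards one arm. The documents do not support that. The CGM arm is asked to return its reader along with the baseline sensor, but nothing indicates that sensor loss differs by arm.

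**On days after allocation.** A reader might infer that the baseline is contaminated by the intervention. It is not: the sensor is blinded, the assigned monitoring and the diet begin together at Day 0, and 8.4 requires baseline assessments to be finished before then. Only anticipatory behaviour remains, and no passage shows any. Section 8.4 does mention medication adjustment, but as one possible reason for a delay between Day −1 and Day 0. It is not described as occurring during sensor wear, as following from allocation, or as differing by arm, so it is not evidence of a shift. The text available does not date disclosure of the arm; the Appendix A schematic and the Appendix C instructions, which could not be seen, may do so. Early randomization also has a practical purpose in a remote trial, because arm supplies must be posted and 8.4 wants a short gap before Day 0.

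**On the evaluable definition.** It is a wording conflict only; the calculation in 15.5 is unaffected.

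**Conclusion.** The exclusion in 15.1 is worded too widely. It removes randomized participants with fewer than five recovered baseline days, including those with a usable Month 3 TIR. At an assumed 5% failure rate this is about 7.5 of 150 randomized, of whom about 6.4 (150 × 0.05 × 0.85) would have a Month 3 value. The power at stake is small: 0.6 points at a correlation of 0.5, 0.9 at 0.3 and 0.2 at 0.7. The reason to change it is to keep the randomized set intact. The failure rates and correlations are assumptions.

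That up to 9 of 14 baseline days (15 of 20 with a pooled repeat sensor) can follow allocation is a fact of timing and a worst case. Bias from it is speculative, probably small and of unknown direction. Taken together, these are clarifications worth considering and do not threaten the primary analysis.

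**What to change.** 1. **Section 15.1, main change.** Limit the exclusion to consented participants who were never randomized. State that every randomized participant with a Month 3 TIR stays in the mixed model even if baseline TIR is missing. This is a change of text only, with no added visits, devices or sample size.

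2. **Section 7.2.** Align the definition of evaluable data with the Month 3 retention on which 15.5 rests. This is also text only.

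3. **Section 15.1, optional.** Prespecify a sensitivity analysis of the primary endpoint that takes baseline TIR only from days before the randomization date, including for anyone with a repeat sensor. It needs the randomization date, and preferably the arm-disclosure date, on record. The cost is a less precise baseline that may rest on five days, the plan's own minimum. With an assumed day-to-day TIR SD s and independent days, the added variance is s²(1/5 − 1/14) = 12.9, 28.9 or 51.4 for s = 10, 15 or 20. At r = 0.5 and 63 per arm the standard error, √((400 + added variance) × 2/63), rises from 3.56 to 3.62, 3.69 or 3.79. Power of the primary analysis is unchanged.

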4.1 Study Objectives

The primary objective of this study is to compare the difference in change in 14-day CGM-derived TIR (% time with glucose 70-180 mg/dL) during Baseline and 3-month Post-Dietary Change periods between participants with T2D who are randomized to use either BGM or CGM to guide dietary and diabetes medication adjustments as part of the Virta Treatment.

The secondary objectives of this study are to compare:

1. Difference in 90-day mean blood ketone levels between BGM and CGM arms
2. Difference in changes in other CGM-derived metrics from Baseline to 3-month Post-Dietary Change period between BGM and CGM arms
3. Difference in percent of participants reaching CGM-derived consensus targets at the end of the 3-month Post-Dietary Change period between BGM and CGM arms
4. Difference in Change in HbA1c from Baseline to the end of the 3-month Post-Dietary Change period between BGM and CGM arms

The exploratory objectives of this study are to describe:

1. Change in CGM-derived TIR during Baseline and 6-month Follow-Up period
2. Change in other CGM-derived metrics during Baseline and 6-month Follow-Up period
3. Percent reaching CGM-derived consensus targets during 6-month Follow-Up period
4. Change in A1c from Baseline to 6-month Follow-Up period
5. Change in diabetes medication use
6. Change in dietary intake
7. Change in body mass index (BMI) and body weight
8. Percent reaching blood ketone targets $\geq 0.5\text{mM}$
9. Mean blood ketone levels
10. Change in CGM-derived ‘time in tight range’ (TITR; glucose 70-140 mg/dL)
11. Absolute values in CGM-derived metrics
12. Number of contacts between participants and Virta care team
13. Change in mean scores on patient-reported outcome (PRO) surveys

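### Five sensor days are the only baseline measure required before open-label randomization, so the baseline distress scale and single diet recall can be completed after the participant knows the arm

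*Combined protocol and SAP*

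**What the plan says.** Three sections give the same trigger for randomization. Section 8.4 states: "Participant is randomized once they confirm that the minimum of five days of Libre Pro CGM data has been recorded". Section 7.2 randomizes "once a minimum of five days of blinded Libre Pro CGM data is confirmed by the participant", and section 8.2 states: "A minimum of five days of blinded Libre Pro CGM sensor data must be obtained for randomization". Consent and eligibility come first, but no other baseline measure is named as a condition.

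The deadline for the remaining measures is separate and later. Section 8.4 states: "All baseline assessments must be completed before Day 0". Section 8.3 adds: "Required assessments can take place anytime during the Contact Period".

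The Protocol Summary places allocation inside the same period: "1:1 randomization to either BGM or CGM during Baseline assessment period". Section 8.4 has arm-specific supplies reaching the participant in Contact Period 1, and 7.2 says that participants will know their arm.

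Appendix B lists the distress survey, the ASA24 recall, medication use and weight under Baseline without placing them before or after randomization. Section 4.2.3 makes all of them exploratory. Dietary intake rests on one recall per time point, and 4.1 includes the objective "Change in mean scores on patient-reported outcome (PRO) surveys". Section 15.3 limits the exploratory analysis to description with a 95% confidence interval for each endpoint and no testing.

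**The concern.** In an open-label trial, a baseline value is protected by randomization only if it is fixed before the participant learns the arm. Here the rules allow the reverse order for two instruments that depend on what the participant says. Someone who hoped for CGM and was assigned BGM, or the other way round, may answer the distress scale differently. The same person may also eat or report differently on the day covered by the recall.

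Such a reaction arises after randomization, so randomization does not balance it. It enters change from Baseline with the opposite sign: a baseline distress score raised by disappointment makes later improvement in that arm look larger. With a single recall there is no earlier diet value to use instead. At stake is how far the distress and diet results can be trusted. Section 3.2 gives diet some weight, because it hopes to show whether CGM influences adherence to dietary guidance.

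**Working it through.** **Order of events, from the text**

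| Event | Earliest or latest time allowed | Section |
|---|---|---|
| Consent, then supplies by mail | within Day -21 to -1 | 8.3, 8.4 |
| Randomization | from five confirmed sensor days | 7.2, 8.2, 8.4 |
| Arm-specific supplies arrive | after randomization, still in Contact Period 1 | 8.4 |
| Distress scale, ASA24 recall | any time in the period, before Day 0 | 8.3, 8.4 |

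Nothing in the readable text puts the last row before the second.

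**Length of the window.** Upper bound: the sensor starts on Day -21 and randomization follows at sensor day 5, which leaves 21 - 5 = 16 days before Day 0. Randomization at sensor day 7 or 10 leaves 14 or 11 days. If consent and mailing take a week (assumed), so that the sensor starts on Day -14, the window is 14 - 5 = 9 days.

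**Plan's sample size, used only to scale the bias.** Section 15.5 assumes a 10-point difference, an SD of 20, two-sided 0.05 and 80% power. The normal approximation gives n = 2 × (1.960 + 0.842)² × (20/10)² = 62.8, so 63 per arm, as stated. An exact t-test gives 63.8, so 64; the difference does not matter here.

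**Bias in change from Baseline.** Let p be the share in each arm who complete the instrument after learning the arm. Let d be the separation between arms, in SD, that this knowledge causes among them. The expected baseline difference is then p × d instead of 0, and the between-arm difference in change is off by -p × d. The documents give neither p nor d, so both are assumed. Absolute bias in SD:

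| p | d = 0.1 | d = 0.2 | d = 0.3 |
|---|---|---|---|
| 25% | 0.025 | 0.05 | 0.075 |
| 50% | 0.05 | 0.10 | 0.15 |
| 75% | 0.075 | 0.15 | 0.225 |

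**Against sampling error.** With 63 per arm and an assumed baseline-to-follow-up correlation of 0.5, the SD of change is √(2 × (1 - 0.5)) = 1 SD. The standard error of the difference in change is then √(2/63) = 0.178 SD. The middle case is 0.10/0.178 = 0.56 standard errors. The extremes are 0.025/0.178 = 0.14 and 0.225/0.178 = 1.26.

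**The case against.** The plan permits late completion but does not say that it will happen. The Appendix A schematic is not shown and the participant instructions in Appendix C are a separate document; either might set the order. That stands, so the point is limited to the readable text.

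Section 15.3 specifies no between-arm contrast for these endpoints and, unlike 15.1 and 15.2, does not say that summaries are by treatment. A reader might infer that the plan will report a biased between-arm estimate with its interval. It does not promise one. The figures above apply to the informal comparison that a two-arm description invites, and they follow entirely from the assumed inputs.

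A reader might also take 16 of 21 days, or 76%, as the usual share of the baseline period after allocation. It is a ceiling that ignores consent and shipping. Section 8.4 also asks that any delay between Day -1 and Day 0 be kept to a minimum, so that gap is not unlimited.

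A stronger reading is that the medication baseline is already contaminated by providers who know the arm. Section 8.4 does list "personal factors for the participant (e.g. scheduling, medication adjustment, CGM wear issues" among the reasons for delay. But 4.2.3 takes medication from the medical record, no section says when providers learn the allocation, the care team cannot see the blinded sensor data (section 8), and arm-specific monitoring starts at Day 0 (8.2). What remains is smaller: the reference date of the Baseline regimen is not defined.

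Section 14 says that REDCap logs all user activity, so late distress surveys could be identified afterwards. The plan does not commit to looking, and identifying them would not recover a clean value.

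**Conclusion.** The point holds for the distress scale and the diet recall. The stated rules allow both to be collected as Baseline after the open-label arm is known, and that can bias the descriptive change in distress and diet. The size is unknown: about 0.03-0.23 SD in an informal between-arm comparison, if 25-75% answer late and knowledge of the arm separates the arms by 0.1-0.3 SD.

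A reader might infer that the trial's main conclusions are threatened. The documents do not support that, because neither instrument enters a primary or secondary test. Some blinded sensor days and the HbA1c draw may also follow allocation, but those are device and laboratory readings, not self-reports, and this point does not rest on them. The undefined date for Baseline medication use and weight is a lesser matter of definition. This is an inexpensive improvement to exploratory measures.

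**What to change.** In 7.2 and 8.4, release the allocation only when two conditions are met: five confirmed sensor days, and completion of the Diabetes Distress Scale and the ASA24 recall. Section 12.1 lets participants leave uncomfortable questions unanswered, so a submitted form with blanks should satisfy the second condition. Record each completion date against the randomization date, flag any value dated later, and do not use it as Baseline. The recall is completed in ASA24 and not in REDCap, so staff would enter its date.

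As a smaller change, define Baseline medication use and medication effect score as the regimen in the record at randomization, and Baseline weight as the last value before it.

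The cost is wording in two sections and a REDCap check. A few participants may be randomized a day or two later. No visit, procedure or sample size is added.
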